4.10.2. COLLECTION OF BLOOD SAMPLE

Approximately 3-4 milliliters of venous blood will be taken from all participants and collected by identified trained blinded medical personnel into a plain tube, sample will be labelled. Similar amount is collected into EDTA tube for HbA1c analysis. The sample is allowed to be at room temperature about 20-30 minutes to allow for clot formation. Centrifugation is then done for 10 minutes; the resultant supernatant is the serum. The serum formed will be transferred into a clean polypropylene tube using Pasteur pipette, the serum is later stored and transported at temperature -70°C or lower.

The sample will be transported to the Immunology Laboratory at Hospital Universiti Sains Malaysia for quantification and analysis of IL-6, processed by a identified trained blinded laboratory personnel.

4.10.3. QUANTIFICATION OF IL-6

[figure not shown]
The serum level of Interleukin-6 is measured using the Human IL-6 ELISA kit with pre-coated serum (LEGEND MAXTM, BioLegend, Inc). The sampling, storage, assay procedures were done according to the kit protocol. The analysis will be conducted in the Biomedical Laboratory and Central Research Laboratory, USM.

4.10.4. REAGENT AND SAMPLE PREPARATION

The 20X Wash Buffer was diluted to with 1X deionized water. Any crystals formed within the 20X Wash buffer will be dissolved by bringing to room temperature and vortex until dissolved. Reconstitute the lyophilized Human IL-6 Standard by adding the volume of Assay Buffer A to make the standard stock solution. Allow the reconstituted standard to sit at room temperature for 15-20 minutes, then briefly vortex to mix completely. Initial testing of biological samples should be performed to determine an optimal concentration that is within the linear range of the standard curve. Dilute samples using Assay Buffer A.

[figure not shown]
4.10.5. ASSAY PROCEDURES

Dilute 12.5 μ L of the standard stock solution in 487.5 μ L of Assay Buffer to create 500 μ L of the 500 pg/mL top standard. Next, Assay Buffer A is used as the diluent and six two-fold serial dilutions are made using the 500 pg/mL top standard in different tubes. Assay Buffer A acts as the zero standard (0 pg/mL), and the human IL-6 standard concentrations in the tubes are 500 pg/mL, 250 pg/mL, 125 pg/mL, 62.5 pg/mL, 31.3 pg/mL, 15.6 pg/mL, and 7.8 pg/mL, respectively. Next, at least 300 μ L of 1X Wash Buffer is used to wash the microplates four times.

50 μ L of Assay Buffer A and 50 μ L of standard dilutions or samples are added to the corresponding wells in each well. After that, the plates are sealed with a plate sealer and

incubated for two hours at room temperature with 200 rpm shaking. After discarding the contents, the plate is cleaned four times using 1X Wash Buffer. After adding 100 µL of Human IL-6 Detection Antibody solution to each well, the plate is sealed and left to incubate for an hour at room temperature while being shaken. After discarding the contents, the plate is cleaned four times using 1X Wash Buffer. Following that, 100 µL of Avidin-HRP After adding a solution, the plate is sealed and allowed to sit at room temperature for half an hour while being shaken. After discarding the contents, the plate is cleaned five times using 1X Wash Buffer. After adding 100 µL of Substrate Solution F to each well, each one is left in the dark for 15 minutes. Human IL-6-containing wells ought to become blue in a way that is proportionate to the amount of the substance present. Each well should contain 100 µL of Stop Solution to stop the reaction, and the resultant solution should turn yellow instead of blue. After 30 minutes, the absorbance at 450 nm wavelength is measured, and the findings are recorded. Sample will be discarded after the completion of data collection and analysis.

4.10.6. DATA COLLECTION AND ANALYSIS

Data recorded in data collection sheet transferred into electronic data and analyzed using Statistical Package for Social Sciences (SPSS), the latest version. The mean serum IL-6 and mean RNFL thickness of both groups will be analyzed using ANOVA repeated measures; within factors and within-between factors. All the p-value of less than 0.05 was considered statistically significant.

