3.1.2. SPECIFIC OBJECTIVES

1. To compare the mean serum level of Interleukin-6 in patients with JOAG with and without honey Kelulut consumption for 3 months.
2. To compare the mean retinal nerve fiber layer thickness in patients with JOAG with and without honey Kelulut consumption for 3 months.

3. To compare the tear break-up time (TBUT) and Schirmer test in patients with JOAG with and without honey Kelulut consumption for 3 months.

4. To compare the level of glycated hemoglobin (HbA1c) level in patients with JOAG with and without honey Kelulut consumption for 3 months.

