4.4. SAMPLE SIZE

Sample size calculation

GPower 3.1.9.7 software was used to calculate the sample size.

The power of the study will be set at 80% with a significance level of 5%.

For the sample size calculation was statistical data used was repeated measures ANOVA within and within between.

The largest sample size was 24.

To account for the attrition rate, 20% was added, which gives a total estimated minimum sample size of 30 per group.

Total sample size: 60 (30 per group)

Objective 1:

To compare the mean serum level of Interleukin-6 before and after consumption of honey Kelulut for 3 months among patients with JOAG.

Calculated sample size: 24

By the addition of 20% drop outs, the sample size that needs to be collected for each group is 30 subjects

Total sample size: 60

Objective 2:

To compare the mean RNFL thickness before and after consumption of honey Kelulut for 3 months among patients with JOAG.

Calculated sample size: 24

By the addition of 20% drop outs, the sample size that needs to be collected for each group is 27 subjects.

Total sample size: 60

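### No outcome is named primary and every p value below 0.05 counts, so the 5% level does not hold across the five outcomes (22.6% if they are independent)

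*Protocol*

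**What the plan says.** Section 3.1.2 gives four objectives side by side:

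- Objective 1: "To compare the mean serum level of Interleukin-6 in patients with JOAG with and without honey Kelulut consumption for 3 months".
- Objective 2: "To compare the mean retinal nerve fiber layer thickness in patients with JOAG", again with and without honey.
- Objective 3 holds two outcomes: "To compare the tear break-up time (TBUT) and Schirmer test in patients with JOAG with and without honey Kelulut consumption for 3 months".
- Objective 4: "To compare the level of glycated hemoglobin (HbA1c) level in patients with JOAG", again with and without honey.

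That makes five outcomes, and nothing in the protocol ranks them. The end point named in section 4.2 is completion of the supplement followed by the final examinations; it is not an outcome variable. Section 4.4 states "The power of the study will be set at 80% with a significance level of 5" per cent and reports a calculated size of 24 for both IL-6 and RNFL, without placing one above the other. Chapter 5 gives each of the five outcomes its own table with a p value.

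Section 4.10.6 sets the decision rule: "All the p-value of less than 0.05 was considered statistically significant". For IL-6 and RNFL it asks for a repeated-measures ANOVA with both the time term and the group-by-time term. It names no model for TBUT, Schirmer or HbA1c. The protocol contains no hierarchy, gatekeeping or adjustment.

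**The concern.** With five outcomes, one shared threshold and no primary, a significant result on any outcome can be presented as the trial's finding. If honey does nothing, the chance that at least one outcome crosses the threshold is well above 5%. A reader of the report could not tell which result was meant to answer the trial's question.

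A second choice lies inside the analysis. The objectives in section 3.1.2 compare patients with and without honey. The nulls for IL-6 and RNFL in section 3.3, the objectives as restated in section 4.4 and the table titles in Chapter 5 are framed as before against after. Because section 4.10.6 asks for both ANOVA terms for IL-6 and RNFL, a change over time could be called significant and read as a honey effect. The time term averages over both arms, so it can be significant when the arms change equally.

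**Working it through.** **Inputs**

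- Per-test level 0.05: sections 4.4 and 4.10.6.
- Number of outcomes k = 5: section 3.1.2 and the Chapter 5 tables. Four of these carry a benefit hypothesis (IL-6 falls; RNFL, TBUT and Schirmer rise). HbA1c is hypothesised not to rise.
- Two-sided testing: assumed, because sidedness is not stated and the nulls are of no difference.
- Correlation between outcomes: not given, so a range is assumed.
- Each single test is taken to hold its own 5% level.

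**The plan's own figure.** For one test, 1 − 0.95 = 5%. The stated 5% is reproduced as a per-test level.

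**Independent outcomes, all nulls true.** The chance of at least one false positive is 1 − 0.95^k.

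| Set | Calculation | Result |
|---|---|---|
| IL-6 and RNFL only | 1 − 0.95^2 = 1 − 0.9025 | 9.75% |
| Four benefit outcomes | 1 − 0.95^4 = 1 − 0.8145 | 18.5% |
| All five outcomes | 1 − 0.95^5 = 1 − 0.7738 | 22.6% |

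**Correlated outcomes.** For k normal statistics with common correlation ρ and c = 1.96, the rate is 1 − ∫ φ(u) [Φ((c − √ρ·u)/√(1−ρ)) − Φ((−c − √ρ·u)/√(1−ρ))]^k du.

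| Assumed ρ | Four outcomes | Five outcomes |
|---|---|---|
| 0.3 | 17.4% | 20.9% |
| 0.5 | 15.6% | 18.3% |
| 0.7 | 13.0% | 14.8% |

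If only TBUT and Schirmer are correlated (0.5) and the rest are independent, five outcomes give 22.0%.

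**False benefit only.** A two-sided 5% test goes wrong in the favourable direction 2.5% of the time. For four independent outcomes this gives 1 − 0.975^4 = 1 − 0.9037 = 9.6%, against 2.5% for one outcome, a ratio of 9.6/2.5 = 3.8.

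**After the change.** With one primary outcome and one comparison, the chance of a false positive on the primary is 5.0%. Testing the secondary outcomes only after a significant primary, in fixed order or with Holm, keeps the chance of any false positive in that sequence at no more than 5%.

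**The case against.** The case on the other side has four parts.

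1. **Separate questions.** Section 3.3 gives each objective its own null, and no rule says the trial succeeds if any one test is significant. Whether separate questions need joint error control is debated. This stands as a caution against treating 22.6% as the error rate of a declared success rule. It does not supply the missing primary outcome.

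2. **Adjustment can be left to an analysis plan.** True of the method. But the protocol does not leave the matter open: section 4.10.6 applies an unadjusted threshold to every p value, and a later adjustment would depart from it. The choice of primary outcome is a design decision for the protocol.

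3. **IL-6 and RNFL already lead in practice.** Sections 4.4, 4.10.6 and 4.10.7 concentrate on these two. That is fair, and for the pair the figure is 9.75%. They are still two outcomes, unranked, and the threshold covers the rest as well.

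4. **The choice of primary is the sponsor's.** This stands. IL-6 is objective 1, but RNFL has the same calculated size in section 4.4.

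Three stronger readings are tempting and not supported. A reader might infer that the protocol promises 5% overall and contradicts itself; section 4.4 gives 5% as a significance level in a power calculation, best read as per test. A reader might infer that every outcome gets two tests, which for four outcomes would give 1 − 0.95^8 = 33.7%; the two ANOVA terms are prescribed only for IL-6 and RNFL. A reader might take 18.5% or 22.6% as the chance of a false claim of benefit; those figures count errors in either direction, and 22.6% includes HbA1c, where a false positive would not be a benefit claim.

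**Conclusion.** The point holds: the protocol names no primary outcome and treats every p value below 0.05 alike across five outcomes, so 5% does not hold across the set. The two-sided chance of at least one false positive is 22.6% for five independent outcomes, falling to about 18% at an assumed common correlation of 0.5. For false benefit on four independent outcomes it is 9.6%, nearly four times the 2.5% for one outcome. In addition, for IL-6 and RNFL the time term offers a route to a significant result that says nothing about honey against no honey.

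The figures assume that all nulls are true, that tests are two-sided and that each single test is valid at 5%. Section 4.6 allocates whole centres to the arms, which bears on that last assumption; it is a separate issue and is not counted here. The defect should be corrected. It does not prevent the outcomes from being measured and reported.

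**What to change.** Before any results are seen:

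- In sections 3.1.2 and 4.10.6, name one primary outcome. IL-6 is the natural candidate as objective 1 and a basis of the sample size, but the sponsor should choose between IL-6 and RNFL.
- Judge it only by the between-arm (group-by-time) comparison at two-sided 5%.
- Label the other efficacy outcomes secondary. Test them after the primary in a fixed order or with Holm, or report them descriptively with 95% confidence intervals.
- Report HbA1c as a safety outcome with its confidence interval.
- State that the time main effect supports no claim of benefit.
- Reword the nulls in section 3.3, the objectives restated in section 4.4 and the tables in Chapter 5 so that they all describe the between-arm comparison. Otherwise the new rule would conflict with the protocol's own before-after nulls.

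The cost is a few sentences, with no added patients or visits. The downside is that the secondary outcomes lose stand-alone claims at 0.05.

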4.10.7. FOLLOW UP

Patients are assessed after a period of 3 months. RNFL thickness and serum IL-6 level will be measured. All these parameters will be measured using the same machine using same techniques. Compliance to the honey supplement will also be tested, by evaluating the diary filled by the patients and the consumed honey packages. Participants who were found to be less than 75 % compliant with the study were excluded from the study.

CHAPTER 5: RESULTS

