3.2. RESEARCH HYPOTHESIS

3.2.1. The mean serum level of Interleukin-6 reduces after consumption of honey Kelulut for 3 months among patients with JOAG.

3.2.2. The mean thickness of retinal nerve fiber layer increases after consumption of Honey Kelulut for 3 months among patients with JOAG.

3.2.3 The tear break-up time (TBUT) and Schirmer test increases after consumption of honey Kelulut for 3 months among patients with JOAG.

3.2.4 The level of glycated hemoglobin (HbA1c) does not increase with the consumption of honey Kelulut for 3 months among patients with JOAG.

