4.5. SELECTION CRITERIA

Inclusion criteria

All JOAG patients age 15 years old and above – 40 years old at the time of diagnosis

Compliant to conventional treatment and achieved target intraocular pressure

Exclusion criteria

Patients with allergy to honey or honey-based products

OCT signal less than 6/10

Concurrent retinal diseases and other optic neuropathies

Systemic neurodegenerative disease

Systemic comorbidities such as diabetes mellitus and autoimmune diseases

Patients on other honey-based products for the last 3 months

Patient who consumes honey-based products during the study duration of 3 months

(monitoring via honey-diary, return of the used sachet during the follow up visits)

Patients on anti-oxidants, traditional medications or herbal products for the last 3 months

Topical usage of steroids, systemic steroids and non-steroidal anti-inflammatory drugs.

Sepsis

Compliance less than 75%.

The duration of treatment with honey will be 3 months (90 days), patient who missed more than 22 sachets of honey will be excluded.

Compliance will be assessed through regular monitoring via monitoring of honey-diary and patients are required to return the used honey sachets during clinic visits.

Withdrawal criteria

All patients who do not receive standard treatment for JOAG

All candidates who develops sudden unexpected severe allergic reaction (SUSAR) to the investigated product.

Participants who withdraw or drop out of the study will not be replaced. Follow-up assessments will continue for all participants, including those who withdraw from the honey supplementation, to allow for comprehensive data collection and minimize loss to follow-up. Throughout the study period, participants will continue their conventional glaucoma medications without interruption to ensure standard clinical care is maintained.

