4.7. HONEY SUPPLEMENT

The honey used in this study is Brainey Madu Kelulut, harvested from *Heterotrigona Itama*. It will be supplied for a total of three months after the recruitment and completion of initial examination and blood sampling. The participants in the ‘no honey’ group did not receive any placebo. Patient in the ‘no-honey’ group is prohibited from consuming products that is based on honey Kelulut or other honey-based products throughout the study period. The control group will consist of matched JOAG patients receiving standard treatment without honey.

Both the patients and the Principal Investigator will not be blinded by the modality of treatment.

Participants were instructed regarding the consumption of the honey by the Principal Investigator. The honey will be supplied in the form of sachet, dosage of 30g per sachet per day for 3 months. The participants are advised to consume the honey at least 30 minutes prior to meals or other medications to avoid any interactions. Participants are also advised not to mix or dilute the honey using other solutions or food products. Participants are also prohibited from consuming other honey-based products throughout

the duration of the study. Those who develop any allergic reaction such as rashes, shortness of breath, wheezing, dysphagia or anaphylactic reactions are advised to immediately discontinue the product and seek immediate treatment from the nearest Emergency Department and contact the Principal Investigator regarding the side effects.

The principal investigator will also advise the patients regarding the compliance to treatment. The compliance will be monitored via a printed diary that will be given upon enrolment. Patients are required to tick on the diary upon completion of the honey sachets daily.

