4.10. DATA COLLECTION AND ANALYSIS

4.10.1. PATIENT RECRUITMENT

The study will be conducted after obtaining approval from the Universiti Sains Malaysia Ethical Committee. Patient from the Department of Ophthalmology Hospital Universiti Sains Malaysia (HUSM), Department of Ophthalmology Hospital Raja Perempuan Zainab II (HRPZ II), Department of Ophthalmology Hospital Sultanah Nur Zahirah (HSNZ) and Department of Ophthalmology Hospital Sultan Ismail Petra (HSIP) will be selected according to our inclusion and exclusion criteria. Participants who fulfilled the selection criteria are identified and provided with the information sheet regarding the study. Written informed consent is obtained from all participants or legal guardian.

The eye with the better visual acuity will be selected to standardize the examination. A comprehensive ophthalmic assessment is done which includes visual acuity, Schirmer test, Tear break-up time (TBUT), intraocular pressure measurement by Goldmann applanation tonometry, slitlamp and fundus examination and gonioscopy using Goldmann three mirror contact lens. OCT macula and RNFL thickness measurement using optical coherence tomography is done after pupillary dilatation by some identified single-blinded trained personnel.

Blood sampling will be taken from all participants, serum separated, stored and transported to HUSM Laboratory and assayed. Quantification of cytokine IL-6 performed using IL-6 enzyme-linked immunosorbent assay (ELISA) kit. The participants were randomized into either ‘honey’ or ‘non-honey’ groups. The honey used in this study is Brainer Madu Kelulut, harvested from *Heterotrigona Itama* supplied for a total of three months after the recruitment and completion of initial examination and

blood sampling. The participants in the ‘no honey’ group did not receive any placebo. After 3 months of honey supplement therapy, participants in both groups were reassessed during follow-up. The mean serum IL-6 and RNFL thickness were re-measured, using the same OCT machine and IL-6 ELISA test kit. Participants who were not compliant to the honey supplement were excluded from the study.

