9.5. PATIENT WITHDRAWAL

The investigators could withdraw the subject, or the subject could withdraw their participation from the study without any penalty or loss of benefits. The reason for withdrawal would be recorded in the Case Report form. Reasons for cessation of study subjects by investigators includes non-compliance with protocol and study requirement and adverse effect towards the drug.

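### Patients are excluded for what they do after allocation (under 75% compliance, other honey use), so the main comparison is in effect per-protocol and conflicts with the promise to follow everyone

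*Protocol*

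**What the plan says.** All references are to the protocol.

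- Section 4.10.7, on the 3-month assessment: "Participants who were found to be less than 75 % compliant with the study were excluded from the study".
- Section 4.5, exclusion criteria: compliance below 75% is listed, and over 90 days a "patient who missed more than 22 sachets of honey will be excluded". The same list contains: "Patient who consumes honey-based products during the study duration of 3 months".
- Section 4.10.1: "Participants who were not compliant to the honey supplement were excluded from the study".
- Section 4.5, withdrawal criteria: "Follow-up assessments will continue for all participants, including those who withdraw from the honey supplementation". The stated aim is to limit loss to follow-up. Withdrawals are not replaced.
- Section 9.5: "Reasons for cessation of study subjects by investigators includes non-compliance with protocol and study requirement and adverse effect towards the drug".
- Section 4.7: the no-honey "group did not receive any placebo", is barred from honey products, and treatment is open to patients and the principal investigator.
- Section 4.10.6 plans a repeated-measures ANOVA of both groups and names no analysis set.

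**The concern.** An exclusion criterion should be decidable before allocation. Sachet count and honey use during the study are decided by the patient afterwards, and may depend on tolerance, side effects, motivation or general health behaviour. The sachet rule filters one arm only, so what remains is honey patients who took at least three quarters of the product against controls with no matching filter. If compliers would have changed differently over three months even without honey, that difference is counted as a honey effect.

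The sections also give sites incompatible instructions. A patient who stops honey early is to be followed under one paragraph of section 4.5 and excluded under the exclusion list of the same section and under sections 4.10.1 and 4.10.7. Whether that patient's 3-month data count could then be settled after the results are known, in an open-label trial. If the patient is not measured, the gap cannot be repaired later. All four outcomes are affected. HbA1c deserves particular care because its hypothesis is one of no harm: "The level of glycated hemoglobin (HbA1c) does not increase with the consumption of honey Kelulut".

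**Working it through.** **1. The plan's own figures**

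- Sachet boundary: 22 missed leaves 68/90 = 75.6% (kept); 23 missed leaves 67/90 = 74.4% (excluded). The sachet rule and the 75% rule agree. At one sachet a day, anyone who stops after 67 or fewer is excluded, whatever the reason.
- Sample size (section 4.4): 24/(1 − 0.20) = 30 per group, which reproduces. The base figure of 24 cannot be reproduced, because no effect size, SD or correlation is given.

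**2. Which arm each rule can reach**

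| Rule | Honey | Control |
|---|---|---|
| Under 75% of sachets | yes | no (no sachets, no placebo) |
| Other honey use during the study | yes | yes, though the monitoring described relies on the diary and returned sachets |

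**3. Bias from the sachet rule.** With two arms and two times, the group-by-time test equals a t-test on change, so units are SD of change. Let q be the share of the honey arm excluded and g the gap in mean change between compliers and non-compliers. With no true effect, the retained honey patients have the complier mean, while controls keep the full mixture:

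bias = complier mean − [(1 − q) × complier mean + q × non-complier mean] = q × g

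Only a gap in *change* matters; a baseline difference cancels. The documents give neither q nor g, so both are assumed. Two-sided type I error at nominal 5%, by noncentral t with 30(1 − q) honey against 30 controls:

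| q | g = 0.25 | g = 0.5 | g = 1.0 |
|---|---|---|---|
| 10% | bias 0.025; 5.1% | 0.05; 5.4% | 0.10; 6.6% |
| 20% | 0.05; 5.4% | 0.10; 6.5% | 0.20; 11.1% |
| 30% | 0.075; 5.8% | 0.15; 8.1% | 0.30; 17.9% |

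The bias can run in either direction. Simulating controls as the true mixture, which widens their spread a little, gives 5.1% to 15.7% over the same grid. A second model, with compliance correlated 0.2 to 0.5 with change and the least compliant 10% to 30% removed, gives bias of 0.04 to 0.25 SD and type I error of 5.2% to 14.1%. All of these treat patients as independent and so ignore allocation by centre.

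**4. Price of keeping everyone.** Read 24 as per group. The standardised difference giving 80% power is then d = 0.826. If non-compliers gain nothing, the difference shrinks to d(1 − q):

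| | q = 10% | 20% | 30% |
|---|---|---|---|
| Diluted difference | 0.744 | 0.661 | 0.578 |
| Power, 30 per arm analysed | 81% | 71% | 60% |
| Power, 24 per arm analysed | 71% | 61% | 50% |
| Measured per arm needed for 80% | 30 | 37 | 48 |
| Per-protocol power (27, 24, 21 vs 30), if unbiased | 86% | 84% | 81% |

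Simulating the 30-per-arm row with non-compliers at zero effect gives 80%, 69% and 57%.

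**The case against.** - **Analysis sets belong in the SAP, which is not shown, and the protocol never uses the term per-protocol.** True, and the label is an inference. But the protocol is not silent: it states three times that such patients are excluded from the study. An SAP that kept them would contradict it.
- **The contradiction is narrow.** Sections 4.10.1, 4.10.7 and the exclusion list agree with one another; the conflict is mainly with one sentence in the withdrawal paragraph. Section 9.5 is permissive. A patient could be measured at 3 months and only then dropped from the comparison. That reading is possible, but the wording is exclusion from the study, and the monthly compliance review in section 4.6 allows earlier removal. The need to clarify stands.
- **The objectives ask about honey consumption for three months, so a comparison among adherent patients is not foreign to the question.** This supports reporting such a comparison. It does not protect it from selection when only one arm is filtered.
- **The magnitudes are assumed and mostly small.** Correct: six of the nine cells are at or below 6.6%, and entry requires compliance with conventional treatment, which should narrow the gap. The case for change rests on the text; the numbers only show what could happen.
- **Clustering is ignored.** Also correct. With two centres per arm the 5% starting point does not hold, and keeping all patients restores less protection than it would under individual randomisation. That is a separate weakness, to which these exclusions add.
- **The power cost depends on reading 24 as per group.** Section 4.4 inflates it to 30 for each group, which supports that reading. If 24 were a total (12 per arm, d about 1.20), power with 30 per arm analysed would be about 98%, 95% and 89% at 10%, 20% and 30% non-compliance.

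**Conclusion.** The concern holds and should be fixed. Following the protocol as written yields a comparison restricted by post-allocation behaviour, with the compliance filter acting on the honey arm alone, and the sections disagree on whether stopping honey means leaving the study. This follows from the text and needs no assumption.

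The size of the bias is unknown. Over the assumed range it runs from negligible (0.025 SD, type I error 5.1%) to serious (0.30 SD, 17.9%, or 15.7% by the mixture simulation), and it becomes serious only when both the excluded share and the gap in change are large. These figures assume independent patients and no true effect.

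**What to change.** 1. State as the primary analysis: every allocated patient with a 3-month measurement, in the allocated arm, whatever the sachet count or other honey use.
2. Attempt the 3-month measurement in everyone, and report by arm how many lack it.
3. Take the 75% compliance rule and the rule on honey use during the study out of the exclusion criteria, and use them to define a secondary per-protocol set.
4. Report that set beside the primary analysis. This matters most for HbA1c, where the hoped-for result is no increase and dilution by non-compliers could hide a rise.
5. Reconcile sections 4.5, 4.10.1, 4.10.7 and 9.5 so that stopping honey, leaving follow-up and being left out of an analysis are three separate things. This needs no change to any clinical stopping rule.

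**Cost.** Mainly wording and one extra analysis set, since section 4.5 already plans follow-up of everyone. The real cost is dilution: with 24 read as per group and no benefit in non-compliers, the power figures in the working apply, and the 80% in section 4.4 should be qualified accordingly. The higher per-protocol power is no argument for the present rule, as it holds only if that contrast is unbiased.
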